## 1 **GENERAL INFORMATION**

### 1.1 **TITLE**

Randomized, double-blind, placebo-controlled clinical trial to evaluate the effect of Raltegravir intensification (1.200 mg QD) on the gut microbiota of chronically HIV-1 infected subject over time: THE RAGTIME STUDY

### 1.2 **CODE**

RAGTIME

### 1.3 **PROTOCOL VERSION AND DATE**

Version 2, 10th February 2017. Any modification of the protocol must also bear the amendment number and date.

#### **1.8 TECHNICAL SERVICES INVOLVED**

Biochemistry, hematology, quantitative HIV-1 RNA levels, HLA typing, CD4 counts will be all performed at Hospital Germans Trias i Pujol.

Analysis of composition, structure and function of the intestinal microbiome will be performed in the IrsiCaixa AIDS Research [REDACTED]

## **2 ABBREVIATIONS**

AE	Adverse event
AEMPS	Agencia Española de Medicamentos y Productos Sanitarios
AIDS	Acquired immune deficiency syndrome
ALT	Alanine aminotransferase
AST	Aspartat aminotransferase
ART	Antiretroviral Therapy
CRF	Case Report Form
CRO	Clinical Research Organisation
DAIDS	Division of acquired immune deficiency syndrome
DNA	Deoxyribonucleic Acid
DSUR	Development update safety report
EC	Ethics Committee
ELISA	Enzyme-linked immunosorbent assay
GCP	Good Clinical Practice
GMP	Good Manufacturing Practice
GI	Gastrointestinal
HBV	Hepatitis B virus
HCV	Hepatitis C virus
HPV	Human papillomavirus
HIV	Human immunodeficiency virus
HLA	Human Leukocyte Antigen
IB	Investigator's Brochure
ICH	International Conference of Harmonisation
IL	Interferon gamma
INSTI	Integrase strand transfer inhibitor
IP-10	Interferon gamma-induced protein 10
I-FABP	Intestinal Fatty Acid Binding Protein
IMP	Investigational medicinal product
INR	International normalized ratio
LPS	Lipopolysaccharide
LBP	LPS-binding protein
LEFSe	Linear discriminant analysis Effect Size
LOPD	Ley Orgánica de protección de datos
MSD	Merck Sharp and Dohme
NNRTI	Non-nucleoside reverse-transcriptase inhibitors

OTU	Operative Taxonomic Unit
PBMC	Peripheral Blood Mononuclear Cell
PI	Protease inhibitor
PICRUSt	Phylogenetic Investigation of Communities by Reconstruction of Unobserved States
RNA	Ribonucleic acid
RAL	Raltegravir
rDNA	Ribosomal Deoxyribonucleic Acid
SmPC	Summary of product characteristics
SAE	Serious adverse event
SUSAR	Serious unexpected adverse reaction
UAE	Unexpected adverse event
UNAIDS	United Nations Program on HIV/AIDS

### **3 BACKGROUND INFORMATION**

The gut microbiome is essential for the maturation of the neonatal immune system and the adequate development and function of adult immune responses. **HIV-1 infection** in children and adults exerts a rapid and severe **depletion of gut-associated lymphoid tissue**, which damages the intestinal barrier, allowing **translocation of gut commensal bacteria** into the systemic circulation. Bacterial translocation causes **chronic inflammation** and **immune activation**, which lead to **immune deterioration** and **premature aging** of HIV-1-infected subjects, including metabolic disturbances, cardiovascular diseases, cognitive disorders and HIV-associated cancers. Persistence of residual HIV-1 replication in the presence of ART has been associated to incomplete HIV-1 suppression in gut lymphatic tissues due to suboptimal tissular penetration of PI/s or NNRTIs.

In previous work in our institute, we have observed that **HIV-1 infection is independently associated with significant reductions in the gut microbiome richness**, which is, in turn, **inversely correlated with systemic inflammation**. Reduced microbial richness, for example, has been associated with intestinal inflammatory diseases as well as with metabolic syndrome, diabetes and obesity and correlated with metabolic markers.

**Recovering bacterial richness might thus have a positive impact on immune activation, chronic inflammation and the overall health of HIV-infected individuals.** However, achieving that goal will possibly require, alongside potential bacterial supplementations, the use of **ART with high penetration into gut lymphoid tissue** to limit as much as possible the continued damage exerted by residual HIV replication on the GALT. Antiretroviral drugs with higher intestinal penetration like raltegravir may be more effective at recovering the intestinal microbiome composition and function than those with lower gut penetration like darunavir or the NNRTIs. Thereby, **raltegravir intensification could be associated with increases in intestinal microbial richness, implying an improvement on intestinal and overall health.**

Despite the lack of evidence on that regard, previous studies from our group and others would favor that hypothesis. Residual HIV-1 replication in plasma can be deterred by ART intensification with raltegravir, which is, in part, due to the high penetration of raltegravir in intestinal tissues. Moreover, raltegravir intensification decreases peripheral CD8 T-cell activation CD45RA (-) and creates a transient CD4 T-cell redistribution, which revert after raltegravir withdrawal.

The project presented here will be the **first prospective, randomized evaluation of the effect of ART on the structure and function of the gut microbiome**. This study provides a unique opportunity to understand the benefits of ART with high intestinal penetration on the gut microbiome. It is thus a key study to understand the bidirectional interactions between the microbiome and the host in people living with HIV/AIDS.

#### **HYPOTHESIS**

1. ART intensification with raltegravir leads to increases in gut bacterial richness, could possibly affect its composition and/or function.
2. The gut microbiome structure and composition correlates with markers of inflammation, coagulation, enterocyte damage and T-cell activation, maturation and immune senescence.

#### **4 TRIAL OBJECTIVE AND PURPOSE**

##### **4.1 PRIMARY OBJECTIVE**

To evaluate the ability of raltegravir intensification to increase gut microbiome richness and modify the gut microbiome composition of people living with HIV receiving stable ART.

##### **4.2 SECONDARY OBJECTIVE**

To correlate changes in the gut microbiota composition and richness with markers of inflammation, coagulation, enterocyte damage, bacterial translocation and T-cell maturation, activation, exhaustion and senescence during raltegravir intensification.

## 5 TRIAL DESIGN

### 5.1 TYPE OF TRIAL

Phase III, prospective, randomized, double-blind, 2-arm, placebo-controlled clinical trial, with a non-authorized investigational medicinal product.

[figure not shown]
### 5.2 DESCRIPTION OF THE DESIGN

The trial was conducted in a sample of 60 chronically HIV-1-infected adults patients on a stable 3-drug ART with PI/r/c or NRTI/NNRTI and HIV-1 RNA suppression <50 copies/mL, will be randomized 2:1 to intensify their current ART with RAL 1200 mg QD (Intensification arm, n=40) vs. placebo (placebo arm, n=20).

Subjects will be followed prospectively during 48 weeks.

# Study overview

Phase III, 2-arm, placebo-controlled, double-blind, randomized, clinical trial

### 5.3 ENDPOINTS

#### 5.3.1 Primary endpoint(s)

- Increase in bacterial richness (observed species) at week 48, relative to baseline (week 0).

#### 5.3.2 Secondary endpoints

- Longitudinal changes in:
  - Gut bacterial composition
  - Gut bacterial function
  - Other estimators of richness and diversity: Chao1, ACE, Shannon, 1/Simpson.
- Association of the gut microbiome composition and richness with:
  - Inflammation: IL-6, IP-10

- Coagulation: D-Dimer
- Enterocyte damage: Intestinal Fatty Acid Binding Protein (I-FABP)
- Bacterial translocation and monocyte activation: LPS-binding protein (LBP), soluble CD14.
- Maturation, activation, exhaustion and immune senescence in CD4+ and CD8+ T-cells: CD3+, CD4+, CD8+, CD45RA, CCR7, CD28, CD27, HLA-DR, CD38, PD-1, CD57.
- CD4 and CD8+ counts
- CD4+/CD8+ ratio
- In case of changes in the microbiome, the quantification of viral reservoir will be done in PBMCs.

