## 8.2 TRIAL DEVELOPMENT

After accepting the participation and meeting selection criteria during the screening visit, patients would be assessed the baseline visit. Study visits would be at screening, entry (BL) and weeks 12, 24 and 48. Visits should be performed within a 2-weeks window.

Blood and fecal specimens will be obtained and stored at the points specified in the flow chart of the study.

Plasma samples and PBMC will be stored at -80°C.

Viral load, CD4 cells count and a complete biochemistry and hematology will be performed at all visits.

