## 8.4 LABORATORY TESTS

Patients will fast for at least 8 hours prior to assessment, in the points specified in the flow chart of the study (section 8.5). The following parameters will be quantified, as needed:

- **Blood count:**
  - Hemoglobin
  - Red blood count
  - Hematocrit
  - White cell blood count
  - Neutrophil count
  - Lymphocyte count
  - Platelets
  - Prothrombin time
- **Blood biochemistry:**
  - Albumina
  - Glucose
  - Urea
  - Creatinine
  - Estimated glomerular filtration rate (CKD-EPI)
  - Ionogramme: sodium, potassium
  - Total Bilirubin
  - Cholesterol (HDL, LDL and total)
  - Triglycerides
  - Liver enzymes: aspartate aminotransferase (AST), alanine aminotransferase (ALT), gamma-GT, alkaline phosphatase
- **Pregnancy test in women (test strip)**

- **Immunology:**
  - CD4 lymphocytes count
  - CD4 lymphocytes percentage
  - CD8 lymphocytes count
  - CD8 lymphocytes percentage
  - CD4/CD8 ratio
  - HLA-DR
- **Virology:** Plasma HIV-1 viral load.
- **Genotypic testing in plasma at virological failure.**
- **Whole blood:** a blood sample (5 x 10 mL EDTA tubes will be collected at each visit, from which irsiCaixa will obtain 4 plasma vials and as many PBMCs as possible). Plasma markers will be assessed by Luminex and or ELISA technology using EDTA-plasma samples. PBMC-associated markers will be analyses using multicolor flow cytometry. In all cases cryopreserved samples, will be stained and acquired on a Fortesa (BD Biociences) cytometer and analyzed using commercial (Flow Jo) and on-site developed software (Ourflow). In case of changes in the microbiome, the quantification of viral reservoir will be done in PBMCs.
- **Stool samples** will be collected at each visit. This will allow accounting for natural variation in gut microbiota composition. Samples will be used for taxonomic and functional / metagenomic analysis of the bacterial and viral microbiome and soluble & cellular markers of immune activation, inflammation and bacterial translocation.

**Note: Before the beginning of the study, all labs will facilitate to the sponsor and to the investigator a list of the reference normal values of the parameters assessed.**

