### 10.1 STATISCAL ANALYSIS

- Taxonomic and functional diversity within (alpha-diversity) and between samples (beta-diversity) will be determined. Rarefaction curves will be generated to evaluate sampling efficiency. Diversity measures, reflecting the richness of the microbiome in terms of number of species and abundance of each species will be calculated. This will enable comparisons between groups and timepoints. Ordination methods including principal component analysis and phylum abundance within individuals will be used to check for significant differences between groups. Bacterial abundance and functional profiles will be analyzed with LEFSe. Univariate correlations involving >2 groups will be done applying ANOVA plus Tukey-Kramer post-hoc tests and Benjamini-Hochberg correction; 2-group comparisons will be performed with the Welch's t-test. The relationship between the microbiome and markers of immune activation, inflammation, tissue damage and bacterial translocation will require the application of nonlinear Kernel regression methods.
- Subjects requiring antibiotics for their clinical management during follow-up will not be excluded from the analyses, but the type, duration and reasons for antibiotic intake will be recorded and taken into account in association analyses. Results in HIV-1-infected subjects will be compared to the gut microbiome profiles of healthy HIV-1-negative individuals previously reported by the EU FP7-funded MetaHIT consortium. We will also use microbial ecology theory to describe ecological networks between microbes and between them and the host (degree distribution, clustering coefficient, distance, centrality, community structure, connectivity index, etc.).

*For extensive examples of microbiome analyses available and performed previously by our group at irsiCaixa, please see: Noguera-Julian, M. et al. Gut microbiota linked to sexual preference and HIV infection. EBioMedicine (2016) <http://dx.doi.org/10.1016/j.ebiom.2016.01.032>.*

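### Observed species, the primary measure, has no named endpoint at weeks 12 and 24 and no model that uses the three on-treatment visits together

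*Combined protocol and SAP*

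**What the plan says.** Section 5.3.1 gives a single primary endpoint: "Increase in bacterial richness (observed species) at week 48, relative to baseline (week 0").

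Section 5.3.2 lists longitudinal changes in gut bacterial composition, in function, and in "Other estimators of richness and diversity: Chao1, ACE, Shannon, 1/Simpson". Observed species is not among them. Sections 8.1.1 and 8.1.2 divide the measures in the same way. Richness appears once more in 5.3.2, under "Association of the gut microbiome composition and richness with" a set of immune and inflammatory markers, but with no visit and no between-arm contrast.

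On sampling, section 8.2 says "Study visits would be at screening, entry (BL) and weeks 12, 24 and 48", and the flow chart in 8.5 ticks stool at baseline and at weeks 12, 24 and 48. Section 8.4 gives the reason: "Stool samples will be collected at each visit. This will allow accounting for natural variation in gut microbiota composition". It adds: "Samples will be used for taxonomic and functional / metagenomic analysis of the bacterial and viral microbiome".

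On analysis, section 10.1 says: "Diversity measures, reflecting the richness of the microbiome in terms of number of species and abundance of each species will be calculated". The next sentence reads: "This will enable comparisons between groups and timepoints". For two-group comparisons it names Welch's t-test. It names no repeated-measures model, baseline adjustment or pooling over visits, for this measure or any other.

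**The concern.** Four other estimators are followed over time from the same stools, while the measure that carries the primary question has a named endpoint at one visit only. This is probably a side effect of the word that introduces the secondary list, but read literally it leaves a hole.

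The stake is precision and credibility, not validity. Section 10.2 sets 40 against 20 patients without a formal sample size calculation. A change based on one final stool carries all the visit-to-visit variation that the repeated sampling is meant to account for. Under sections 6.7 and 10.1, patients given antibiotics during follow-up stay in the analyses, so a course shortly before week 48 could affect a patient's only on-treatment sample for the primary endpoint. If an early or averaged richness result is reported without having been specified, readers cannot tell it from a choice made after seeing the data.

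**Working it through.** The plan states no power, standard deviation, within-patient correlation or time course for richness, so there is no figure to reproduce.

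**Inputs from the plan:** 40 vs 20 patients (5.2, 10.2); post-baseline visits at weeks 12, 24 and 48 (8.2, 8.5).

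**Assumptions, not in the documents:** equal variance at each visit, scaled to 1; the same correlation r between any two visits; two-sided 5% level; 80% power; no dropout; normal approximation. Sequencing at weeks 12 and 24 is inferred from sections 8.1.2 and 8.4 and from the longitudinal endpoints. It is not stated visit by visit.

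**Step 1. Change scores, closest to the documented analysis.**
- Week 48 minus baseline: variance 2(1 − r).
- Mean of three visits minus baseline: (1 + 2r)/3 + 1 − 2r = (4/3)(1 − r).
- Ratio: (4/3)/2 = 2/3 for every r. The standard error ratio is √(2/3) = 0.816, and 1/(2/3) = 1.5 times the patients.
- Week 12 or week 24 taken alone also has variance 2(1 − r). Listing those visits separately adds no precision; only pooling does.

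**Step 2. Baseline adjustment in both analyses.** Week 48: 1 − r². Mean of three: (1 + 2r)/3 − r².

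| r | Week 48 | Mean of three | Variance ratio | Equivalent patients |
|---|---|---|---|---|
| 0.3 | 0.910 | 0.443 | 0.49 | 2.05 |
| 0.5 | 0.750 | 0.417 | 0.56 | 1.80 |
| 0.7 | 0.510 | 0.310 | 0.61 | 1.65 |

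**Step 3. Another correlation structure.** With serial correlation of 0.3 to 0.9 per 12 weeks, the standard error ratio runs from 0.77 down to 0.66 for change scores and lies between 0.64 and 0.69 with baseline adjustment. The mean had the smaller standard error under every structure tried.

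**Step 4. Detectable difference at 40 vs 20.** (1.960 + 0.842) × √(1/20 + 1/40) = 0.767 standard deviations of the week-48 change. For the three-visit mean in Step 1, 0.767 × 0.816 = 0.626 of the same unit.

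**Step 5. Dependence on the time course.** The mean gains power only if the average effect over visits, divided by the week-48 effect, exceeds the square root of the variance ratio. That break-even is 0.816 for change scores and 0.70, 0.745 and 0.78 with baseline adjustment at r = 0.3, 0.5 and 0.7. The table uses change scores and equal correlation; an effect of 1 is the size that gives the week-48 analysis 80% power.

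| Effect at weeks 12, 24, 48 | Average effect | Power, week 48 | Power, mean of three |
|---|---|---|---|
| 1, 1, 1 (sustained) | 1.00 | 80% | 93% |
| 0.25, 0.5, 1 (linear build-up) | 0.58 | 80% | 52% |
| 0, 0, 1 (late only) | 0.33 | 80% | 21% |
| 1, 1, 0.5 (fading) | 0.83 | 29% | 82% |

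A linear build-up gives (0.25 + 0.5 + 1)/3 = 0.58, below every break-even value above.

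**The case against.** A reader might infer that the trial throws away its week-12 and week-24 data, or gives up its most precise estimate of the raltegravir effect on richness. The documents do not support either.

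On the data, section 10.1 plans to calculate richness as a number of species, which is the primary measure, and expects comparisons between groups and visits. Section 8.4 ties repeated stools to natural variation. Section 8.1.1 names observed species without restricting it to week 48. The secondary objective in 4.2 refers to changes in richness during intensification. Chao1 and ACE are already followed over time, so richness at weeks 12 and 24 is not without an endpoint; one index of it is.

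On precision, the visit average is a different quantity from the week-48 effect. The two agree if the effect is constant from week 12, and the documents give no time course. Under linear build-up or late onset the average is the weaker analysis. The multipliers of 1.65 to 2.05 also presuppose a baseline adjustment that the plan does not name; 1.5 is nearer to what it describes.

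A single pre-specified week-48 primary time point is also legitimate, and section 10.2 declares the study an exploratory pilot. The absence of a longitudinal model affects every endpoint, not just the list in 5.3.2.

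All of this stands, and it limits the size of the point. It does not remove it: section 10.1 allows comparisons over time but fixes no visit, contrast or model for the primary measure.

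**Conclusion.** The point holds as a minor gap in specification. Observed species lacks endpoint status at weeks 12 and 24, and no stated analysis adjusts for baseline or combines visits. The week-48 primary endpoint is unaffected.

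For a sustained effect, the available gain is a one-third cut in variance with change scores, or 39% to 51% when both analyses are baseline-adjusted. These figures rest on assumed equal correlation between visits (r = 0.3 to 0.7 for the adjusted range), equal variances, no dropout, and sequencing at each visit. Because the gain turns into a loss if the effect builds slowly, the average can support the week-48 result but should not replace it.

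**What to change.** Keep week 48 as primary. In section 5.3.2, add observed species at weeks 12, 24 and 48 to the longitudinal secondary endpoints. In section 10.1, pre-specify one baseline-adjusted repeated-measures model for observed species that reports, each with a 95% confidence interval:
- the arm difference at week 48;
- as supportive, the arm difference averaged over weeks 12, 24 and 48.

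State that week 48 governs the conclusion if the two disagree, and confirm that stools from all four sampling visits will be sequenced.

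The cost is a few lines of text and one model. If sequencing at each visit is as inferred, no further visits, samples or assays are needed. The drawback is that the average understates an effect that builds slowly, so it remains supportive.

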## 5.4 MEASURES TO AVOID BIAS

### 5.4.1 Randomization

Once eligibility has been confirmed, study participants will be assigned sequentially into the two treatment groups (intensification with RAL or placebo) through a randomization schedule based on the randomization plan using dedicated computer software.

Merck Sharpe & Dohme Co. will provide to the un-blinded correspondent with the CID randomization schedule that will list the grouping description and ID number. The randomization will be centralized in the CRO FLS-Research Support. The investigator

will phone to the CRO to inform about the eligibility of a patient and if he/she is on treatment with PI/r/c or NRTI/NNRTI-based. The CRO will add the patient to the randomization list, they will assign a code number to the patient and will inform to the Pharmacy Service the group where the patient has been assigned.

The distribution between the branches A (intensification with RAL) and B (placebo) will be 2:1.

It will be impossible for the investigators to know which group will be assigned to a patient before his/her inclusion in the study.

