### 5.4.2 Stratification

Randomization will be stratified by type of ART (PI/r/c or NRTI/NNRTI-based) and CD4 nadir (> 300 or < 300) at screening. In this way, the distribution of these parameters between the study groups will be balanced.

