## 8.3 CLINICAL RECORD AND PHYSICAL EXAM

Demographic and HIV infection-related data will be collected in order to characterize the study population: sex, age, time since HIV diagnosis, risk factor and history of opportunistic infections or tumors, active acute or chronic diseases related or not with HIV-infection, date and type of past surgical interventions, ART history, nadir and current CD4+ counts, HBV or HCV co-infection, history of HPV infection, allergies, current abdominal transit, history of altered abdominal transit, current or past antibiotic therapy, dosing and duration of antibiotic therapy during the previous 6 months.

Patients will be asked for all medication, antiretroviral or not, that he/she may have taken (including over the counter medication), within one week before inclusion and during the study.

A complete physical examination will be performed at the baseline visit, including weight and height. In the follow-up, a physical exam will be performed according to patient's symptoms.

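### Randomisation is stratified by ART type and CD4 nadir, but section 10.1 names an unadjusted Welch's t-test: no bias, but an avoidable loss of power if the factors are prognostic

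*Combined protocol and SAP*

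**What the plan says.** Section 5.4.2 states that randomisation will be "stratified by type of ART (PI/r/c or NRTI/NNRTI-based) and CD4 nadir (> 300 or < 300) at screening", and adds: "In this way, the distribution of these parameters between the study groups will be balanced". Two factors with two levels each make four cells. Sections 5.2 and 10.2 give 60 patients at 2:1, 40 on raltegravir and 20 on placebo.

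The primary endpoint in section 5.3.1 is the increase in observed species from baseline to week 48. Section 10.1 does not name a test for it in particular. The applicable statement is general: "2-group comparisons will be performed with the Welch's t-test". Neither section 10 nor section 10.1 mentions a term for ART type or nadir. The only covariate-like handling in section 10.1 is of antibiotic use, in association analyses. Section 10.2 calls the study a pilot without a formal sample size calculation.

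On the allocation step, section 5.4.1 says patients are assigned "through a randomization schedule based on the randomization plan using dedicated computer software". The investigator phones the CRO to "inform about the eligibility of a patient and if he/she is on treatment with PI/r/c or NRTI/NNRTI-based", after which "The CRO will add the patient to the randomization list". Nadir is not named in the call. The site does hold it: section 8.3 collects "ART history, nadir and current CD4+ counts".

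**The concern.** Stratified allocation makes the arms more alike on the stratification factors than simple randomisation would. If those factors predict the outcome, the true sampling variance of the difference between arms falls. A two-sample test that ignores the strata does not see this. It still counts the spread between strata as noise, so its standard error is too large, its type I error falls below the nominal level and some power is lost. The trial has gone to the trouble of stratifying and then names an analysis that does not use it. With 20 placebo patients there is little precision to spare.

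The allocation call raises a smaller question. If the CRO received only what section 5.4.1 lists, it could separate the two ART levels but not the two nadir levels, so it could identify none of the four cells. The balance on nadir promised in section 5.4.2 depends on a step that the protocol does not describe.

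**Working it through.** **Figures in the plan.** There is no alpha, power, effect size or SD to reproduce. The only arithmetic, 60 at 2:1 = 40 + 20, is consistent.

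**Inputs.** From the documents: 40 and 20 patients, and two binary stratification factors. Assumed, because the documents are silent: a two-sided 5% level; ART split 50/50; low-nadir share 10%, 30% or 50%; factor effects of 0, 0.5 or 0.8 residual SD each; treatment effect 0.8 residual SD; stratified 2:1 blocks of 6; no dropout.

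**Step 1: standard error with adjustment.** In residual SD units, SE = sqrt(1/40 + 1/20) = sqrt(0.075) = 0.274.

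**Step 2: standard error that Welch's test uses.** A binary factor with effect b and share p adds b²p(1−p) to the within-arm variance. At b = 0.5 with both shares 50%, the variance is 1 + 2 × 0.25 × 0.25 = 1.125 and SE = sqrt(1.125 × 0.075) = 0.290. At b = 0.8 it is 1 + 2 × 0.64 × 0.25 = 1.32 and SE = 0.315. With the factors balanced by allocation, the true SE stays close to 0.274.

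**Step 3: consequence, normal approximation.** The effective critical value is 1.96 × sqrt(1.125) = 2.08 at b = 0.5 and 1.96 × sqrt(1.32) = 2.25 at b = 0.8. The type I errors are about 3.8% and 2.4%. At a 0.8 SD effect, 0.8/0.274 = 2.92. Power is then Φ(2.92 − 2.08) = 80% and Φ(2.92 − 2.25) = 75%, against Φ(2.92 − 1.96) = 83% adjusted.

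**Step 4: simulation with t distributions and imperfect blocks.** There were 12,000 runs for type I error and 4,000 for power. The three entries are low-nadir shares of 10% / 30% / 50%.

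| Effect per factor | Type I, Welch | Type I, adjusted | Power, Welch | Power, adjusted |
|---|---|---|---|---|
| 0 | 5.0 / 4.9 / 5.0% | 5.1 / 4.9 / 5.0% | 80.9 / 81.9 / 81.1% | 81.4 / 82.2 / 81.7% |
| 0.5 SD | 4.3 / 3.9 / 4.2% | 5.1 / 4.9 / 5.3% | 79.3 / 78.5 / 77.1% | 81.9 / 82.1 / 81.5% |
| 0.8 SD | 3.3 / 2.7 / 2.7% | 4.7 / 4.8 / 5.0% | 74.8 / 72.0 / 72.1% | 81.8 / 81.6 / 82.4% |

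The pattern matches step 3. A separate simulation held total variance fixed, with four equal cells of 15 allocated 10:5 and a full set of stratum terms. If the strata explain 10%, 20% or 30% of the variance, Welch's type I error is 4.1%, 2.7% or 1.9%. Power at a 0.767 SD difference is 79%, 80% or 82%, against 83%, 87% or 91% adjusted.

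**Step 5: if nadir were not used at allocation.** This is a hypothetical; the documents do not say so. The difference between arms in low-nadir share would then be hypergeometric and move in steps of 1/20 + 1/40 = 7.5 points. The chance of 22.5 points or more is 1.3%, 8.3%, 13.4% and 17.0% at assumed shares of 10%, 20%, 30% and 50%. If low and high nadir differed by an assumed 0.5 SD, a 22.5-point imbalance would move the estimate by 0.225 × 0.5 = 0.11 SD, or 41% of the SE (0.1125/0.274). A model with a nadir term removes this shift, so the same analysis serves both cases.

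**Step 6: why main effects only.** With a 50/50 ART split and a 10% low-nadir share, two of the four cells average 60 × 0.5 × 0.1 = 3 patients. In about half of the simulated trials at that share, at least one cell had no placebo patient.

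**The case against.** Section 5.4.2 states the two-factor rule without qualification, and the description of the call in section 5.4.1 is not said to be exhaustive. A CRO told to stratify on nadir would ask for it, and the randomization plan that section 5.4.1 cites, which is not among the documents, may spell this out. This objection stands. A reader might infer that sections 5.4.1 and 5.4.2 contradict each other, or that patients were allocated without regard to nadir. The text supports neither: it shows an item not mentioned in one sentence, which is a matter of drafting.

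The power figures rest on assumed prognostic strengths and give ART type the same effect as nadir. That also stands. At a 10% low-nadir share and 0.5 SD per factor, nadir adds 0.25 × 0.09 = 0.0225 to the variance and ART type adds 0.0625, so most of the gain there comes from ART type, which the call already reports. At 0.5 SD per factor the gain is only about 3 to 4 points.

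The study is an exploratory pilot, and an unadjusted test errs on the safe side. This limits the weight of the point but does not remove it, since adjusting costs almost nothing even if the factors turn out to be irrelevant.

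**Conclusion.** A minor point, and an inexpensive improvement. Section 10.1 names an unadjusted test for a comparison that section 5.4.2 stratifies. If each factor is worth 0.5 SD, Welch's test runs at about 4% type I error and 77-79% power, against about 5% and 81-82% adjusted. At 0.8 SD each, it runs at about 3% and 72-75%, against about 5% and 82%. If neither factor matters, power differs by less than one point. These figures assume four-cell blocks of 6, a 50/50 ART split, low-nadir shares from 10% to 50%, a 0.8 SD treatment effect and complete data. The direction does not depend on these choices so long as allocation balances prognostic factors; the size does.

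A reader might go further and infer that the comparison is biased or that false positives are inflated. Neither follows. Allocation is random and central, investigators cannot foresee it (section 5.4.1), and ignoring the strata makes the test conservative. The wording of the call and the treatment of a nadir of exactly 300 are clarifications only.

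**What to change.** In section 10.1, state that the between-arm comparison of week-48 change in observed species uses a linear model with treatment and main effects of ART type and CD4 nadir category. Use the stratum values recorded at randomisation or, if nadir was not used at allocation, the nadir recorded in the clinical record under section 8.3. The cost is one sentence, two degrees of freedom and no new data.

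As drafting clarifications, add CD4 nadir in section 5.4.1 to the items the investigator reports to the CRO before allocation, and in section 5.4.2 assign a nadir of exactly 300 to one of the two levels and give the unit. The site already records nadir, so this needs only a phrase in each section and one field on the call form. How the CRO builds its list can be left to the randomization plan.
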